et al, 2005; Chadwick et al, 2009; Langer et al, 2012; Chien & Thompson, 2014). In Chadwick's most recent study (2016), which was the first RCT of group CBTp for voices, there was no significant effect on the primary outcome of psychological distress targeting people with distressing voices in a pragmatic randomized controlled trial. Though there was improvement in intensity of voice distress post-treatment, no effects on depression were found. The generalizability of the study is doubtful across other psychotic symptoms as distressing voices is only one of disturbing symptoms in the course of psychotic disorders.

[figure not shown]

Figure 1 The working mechanism of mindfulness to emotional distress in psychosis

The knowledge gap

Evidence on the effectiveness of mindfulness interventions for psychosis is inconclusive despite that the aforementioned studies have indicated that mindfulness approaches are associated with a decrease in distress, emotional dysregulation and social functioning. Most of the studies had very small number of participants, using non-randomized, non-controlled and inconsistent protocols and process regarding the mindfulness interventions. Particularly, the evidence of mindfulness interventions for regulating emotional dysregulation (such as anxiety, depression and hopelessness) in relation to positive and negative symptoms has not been addressed in the literature.

The knowledge gap is that there is no evidence on whether mindfulness-based intervention can have an effect on emotional distress and emotional regulation in patients with psychosis and subsequently alleviate the positive symptoms of these patients.

Study Aim, Objectives and Hypotheses

The aim of this controlled trial is to test the effectiveness of a mindfulness-based intervention for people with recent-onset psychosis in improving their emotional distress and in so doing this will have a positive effect on positive and negative symptoms, as well as psychosocial functioning.

It is hypothesized that in comparison to routine psychiatric care with Psychoeducation for Psychosis (PEp), the participants receiving Mindfulness-based Cognitive Therapy for Psychosis (MBCTp) will have significantly: -

- Primary outcomes: Decrease in emotional distress at 1-week, 3-month and 6-month follow-ups post-treatment.

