Sample size has been estimated on the basis of previous clinical trials of mindfulness interventions for people with psychosis, in which the primary outcome of depression and anxiety (effect size=0.76), and distress relating to psychotic symptoms (effect size=0.50) were the main outcomes (White et al., 2011; Chadwick et al., 2016). Study power calculation indicated that 82 participants (n=41 per group) were required to detect statistically significant differences on emotional distress between two groups with effect size of 0.63 at post-intervention, p=0.05 and power of 0.80 (Stevens, 2009). Taking account of a 15% attrition, the total sample size required should be 95 (n=48 per group).

Interventions

MBCTp will be delivered to the study groups while PEp will be delivered to the control groups. Intervention groups will be facilitated by the researcher who is experienced in cognitive therapy and mindfulness. The psychoeducation group will be conducted by a research assistant (RA1) who is an experienced psychiatric nurse and is trained by the researcher and an experienced psychoeducation researcher. All sessions will consist of 12-weekly 1.5- hour sessions, plus 12-week practice at home with guided CDs which comprises short mindfulness practice (Chadwick et al, 2016). Mindfulness practice will be with guided verbal instructions offered every couple of minutes to avoid prolonged silence. Mandatory individual home practice will be devised and completion of homework will also be assessed by counting the number of submissions and percentage of

completion per program. The session content will be protocolled according to the origins of MBSR (Kabat-Zinn, 2013) and MBCT (Teasdale, Williams and Mark, 2014) (Appendix 1). It will also be validated by a panel of experts including psychiatrists, clinical psychologists and psychiatric nurses who are experienced in mindfulness and cognitive therapy. Psychoeducation (psychosis) (PEp) will be developed based on the manuals produced by the Early Psychosis Prevention and Intervention of the Early Psychosis Prevention and Intervention Centre (EPPIC) National Support Program (ENSP), Australia and the psychoeducation manual produced by the Foundation for Life Sciences, University of Technology Sydney, Australia (Creek et al, 2015; Perry et al, 2012). It will be validated by a panel of experts and previewed by 5-10 service users in the pilot study.

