To ensure treatment fidelity, three to four sessions will be randomly audio-recorded per intervention group to make up a full program for progress evaluation and commented by an experienced psychiatrist who has been practicing mindfulness and cognitive therapy for over 10 years based on the validated manualized protocol and the Mindfulness-Based Interventions Teaching Assessment Criteria (MBI:TAC) (Crane et al, 2013). The attendance and dropping-out of patients in both treatment and active control group will be continuously monitored by the researcher.

Outcome Evaluation

The primary outcome will be the Depression Anxiety Stress Scale- Short form (DASS-21) (Lovibond & Lovibond, 1995). It is chosen as the primary outcome measurement because scales of anxiety and depression possess the capacity to differentiate from the related state of tension and stress linking with environmental demands and emotional and physical disturbance. It is a 21-item instrument that measures over the past week symptoms of depression, anxiety and stress rated by 4-point severity or frequency scale. The scale is from 0 (did not apply to me at all) to 3 (applied to me very much or most of the time). Internal consistency for each scale for the DASS normative sample are as follows: Depression $\alpha=0.91$; Anxiety $\alpha= 0.84$; Stress $\alpha=0.90$. The phi coefficients of the Chinese DASS-21 version are as follows: Beck Depression Inventory and Beck Anxiety Inventory are Depression-Anxiety 0.81; Anxiety-Stress 0.88 and Depression-Stress 0.83 (Moussa, Lovibond and Laube, 2001).

The secondary outcome measures will be including:

The Emotion Regulation Questionnaire (ERQ) (Gross and John, 2003) is a 10-item scale that was developed to measure participants' tendency to regulate their emotions in cognitive reappraisal and expressive suppression. Items are scored on a 7-point Likert scale ranging from 1 (strongly disagree) to 7 (strongly agree). The internal consistency reappraisal items are from $\alpha= 0.75 - 0.82$ while suppression items are from $\alpha= 0.68 - 0.76$. The reliability for reappraisal and suppression is $\alpha=0.79$ and $\alpha=0.73$ respectively.

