Five Facet Mindfulness Questionnaire (FFMQ) (Baer et al, 2006) is a 39-item self-report questionnaire that measures five facets of mindfulness: observing; describing; acting with awareness; non-judging and non-reacting. The internal consistency for each of the five facets are $\alpha=0.83$, $\alpha=0.91$, $\alpha=0.87$, $\alpha=0.87$ and $\alpha=0.75$ accordingly. Items are scored on a 5-point Likert scale ranging from 1 (never or very rarely true) to 5 (very often or always true). The Chinese version of the Five Facet Mindfulness Questionnaire (FFMQ-C) obtained a good test-retest reliability (0.88) and a high internal consistency (0.83 in the community sample and 0.80 in the clinical sample) (Hou, Wong, Lo and Mak, 2013). A short form scale of the FFMQ (FFMQ-SF) is highly and significantly correlated with the FFMQ-C ($r=0.96$), and explained 91.3% of the variance of the FFMQ-C which will be adapted for the purposes of the study.

The last outcome assessment will be the number and length of re-hospitalization referenced from the case files and self-reporting.

Regarding the qualitative data obtained by focus group interviews, it will be used to determine the common themes being mentioned most frequently by participants and organized under different categories such as expectations, positive and negative outcomes, personal difficulties, positive and negative comments about the program and description.

Data collection procedure

There will be two research assistants (RA), RA1 will be responsible for conducting the psychoeducation program and RA2 will be blinded and doing data collection. The RA2 will conduct the baseline measurements after obtaining the written consent and following comprehensive explanations about the study purpose and procedure and its ethical issues. After that, the participants will be assigned randomly to either study group or control group. Patients' outcomes at the ICCMWs will be measured at one week post-intervention using the same set of questionnaires as the baseline measures.

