Two groups of 3-4 participants in treatment group will be interviewed in a quiet interview room in the ICCMWs, or as preferred by the participants. Participants with significant positive changes, minimal changes and negative changes will be invited according to the baseline and Post-test 1 measurement. Interviews in a focus group format will be conducted to identify the strengths and limitations and therapeutic components from the participants' perspective. Interview questions will be developed based on an open and broad basis criterion (Appendix 2). Audio-recorded group sessions will also be used to examine the group process/dynamics and participants' involvement and appraisals of the group program.

The outcome measurements will be completed by the participants at three and six months after the interventions with the help of RA1 who will be blind to the participants' assigned groups. By self-reporting or case files reviewing, re-hospitalizations of the participants will also be examined and calculated and checked against their medical records. Participants' recruitment, interventions, data (outcomes) collection, and data analyses are outlined in a flow diagram of Appendix 3, as recommended by the latest CONSORT statement.

Data Analysis

Intention-to-treat (ITT) analyses (Fisher et al, 1989) will be used to provide a more conservative estimate of outcomes. By using IBM SPSS, version 23.0, all data on participants' socio-demographic illness-related characteristics, attendance and completion rate, and study outcomes will be numerically coded, summarized and analyzed. Repeated-measures ANOVA tests will be used to assess any significant differences on all dependent (outcome) variables within and between groups and across three post-tests (one week, 3 months and 6 months follow-up).

Sub-group analysis for participants who will complete all sessions and those completers, and the outliers which can have deleterious effects on statistical analyses will also be screened. Defined completers will be those who have attended at least eight sessions by which the main themes of the program are covered (Nose, Barbui and Tansella, 2003).

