Mediation analyses will be conducted to examine covariates of change in emotions and distress associated with psychotic symptoms by multiple regression analysis. Within – subjects effect sizes will also be reported based on Cohen's d statistic. Kaplan Meier survival analysis will be used for the analysis of re-hospitalization rates across treatment and control groups. The significance level of all statistical tests will be set at 5%. Clinical significance will be all subscales of DASS-21 shows a percentage improvement in mean scores in the range of approximately 45–55% pre- and post-intervention (Ng, Trauer, Dodd, Callaly, Campbell and Berk, 2007). For example, the mean DASS severity ratings of depression in pre-intervention is 31.2 and 16.2 in a week post-intervention. The difference is 15.0 and the percent change is 48.1 which is clinical significant. Reliable Change Index (RCI) will take into account the reliability of assessment instrument on scores of each participant between the pre-test and one post-test divided by the standard error of the difference between the two scores. Any value of RCI >1.96 (at p<0.05) will be considered statistically significant (Jacobson & Truax, 1991).

NVivo will be used to analyze the qualitative data on subjective experiences to mindfulness and acceptability to the interventions (Krippendorff, 2004). All audio-taped interviews will be transcribed into Cantonese/Chinese by the research assistant and checked for accuracy of transcription by the researcher. The revised transcripts

will be coded independently and important manifest and meanings in the data will be identified.

Ethical considerations

Approval for human subject research will be obtained from the three ICCMWs and Edinburgh Napier University before the start of data collection. The researcher will ensure and inform the potential participants that participation in the study is voluntary and that withdrawal from the study at any time will not affect any aspects of care. The information leaflet and consent form will be developed according to the format recommended by School of Health and Social Care ethics committee. All participants will be assured of the confidentiality of the data provided and the anonymity of their personal identity, and asked for permission to tape record the interviews and intervention sessions if selected. All data will be safely kept in a locked cabinet accessible only by the researcher.

Adverse events reporting and monitoring

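### ITT is promised, but the only between-arm test of DASS-21, a repeated-measures ANOVA over three post-tests, has no missing-data rule, no named treatment term and no stated baseline adjustment

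*SAP*

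**What the plan says.** The primary outcome is DASS-21 (Outcome Evaluation). Under Study Aim, Objectives and Hypotheses, the primary hypothesis covers all three follow-ups without ranking them: "Decrease in emotional distress at 1-week, 3-month and 6-month follow-ups post-treatment".

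Under Data Analysis, ITT analyses "will be used to provide a more conservative estimate of outcomes". The software is SPSS 23, and the method for every outcome is: "Repeated-measures ANOVA tests will be used to assess any significant differences on all dependent (outcome) variables within and between groups and across three post-tests". The three post-tests are one week, 3 months and 6 months.

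The sample size rests on a different quantity. It is set to "detect statistically significant differences on emotional distress between two groups with effect size of 0.63 at post-intervention", which gives 41 per group. On loss it says: "Taking account of a 15% attrition, the total sample size required should be 95 (n=48 per group").

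Baseline is measured before randomisation, and the one-week assessment is made "using the same set of questionnaires as the baseline measures". In the analysis the pre-test score is used for percentage change and for the Reliable Change Index, which compares "scores of each participant between the pre-test and one post-test". It also helps to select focus-group members. No adjustment of the between-arm test for baseline is stated.

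The other named methods are Kaplan-Meier for re-hospitalisation, regression for mediation, within-subject effect sizes and a completer subgroup. None is a between-arm test of DASS-21 in the randomised population. The completer definition concerns sessions attended, so it is not a rule for missing scores.

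**The concern.** The primary result rests on one sentence, and three things in it are open.

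- **Missing scores.** Classical repeated-measures ANOVA needs every occasion. Someone who misses month 6 would also lose a week-1 score already collected. The analysed set would then be those with complete follow-up, not everyone randomised. The allowance for attrition protects power but not against bias. Nor is a complete-case result reliably conservative, because its bias can run either way.
- **Treatment term.** The sentence implies a group factor and a time factor. It does not say whether the group main effect or the group-by-time interaction decides success. Neither is the post-intervention difference on which the trial is sized.
- **Baseline.** It could be a fourth time level, a covariate or absent from the model. An unadjusted comparison is valid but less precise.

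At stake is whether the primary conclusion depends on choices made after the data are seen, and on who happened to complete all visits.

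**Working it through.** **Inputs from the SAP.** d=0.63, 5% level, 80% power, 41 per group, 15% attrition, 95 in total (Sample size); three post-tests (Data Analysis).

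**Assumptions.** Two-sided test; equal correlation r of 0.4, 0.5 or 0.6 between any two occasions; unit SD. The one-week visit is taken as post-intervention. Effects are either sustained (d, d, d) or fading (d, d/2, 0), and zero at baseline.

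**1. The plan's own figure.** For a two-sample t-test the noncentrality is d/√(2/n) = 0.63/√(2/41) = 2.85, giving power 80.5%. So 41 per group reproduces, as a test at a single time point. (A one-sided test would need only 32.)

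**2. Group main effect over three post-tests.** The variance of the mean is (1+2r)/3. At r=0.5 the noncentrality is 0.63/√(0.667×2/41) = 3.49 if sustained. The mean effect if fading is 0.315, giving 1.75.

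**3. Group-by-time.** The noncentrality is (n/2) × S/(1−r), where S is the sum of squared deviations of the visit effects, with k−1 and (k−1)(2n−2) degrees of freedom for k occasions. Here d² = 0.397.
- Three post-tests, sustained: S = 0
- Three post-tests, fading: S = 0.5d² = 0.198
- Baseline as fourth level, sustained: S = 0.75d² = 0.298
- Baseline as fourth level, fading: S = 0.6875d² = 0.273

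**4. One-week contrast adjusted for baseline.** The variance is 1−r². At r=0.5 the noncentrality is 0.63/√(0.75×2/41) = 3.29.

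Power at r = 0.4 / 0.5 / 0.6:

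| Test | Sustained | Fading |
|---|---|---|
| Group main effect, three post-tests | 95 / 93 / 91% | 44 / 41 / 38% |
| Group-by-time, three post-tests | 5 / 5 / 5% | 63 / 72 / 81% |
| Group-by-time, baseline as fourth level | 76 / 84 / 92% | 72 / 80 / 89% |
| One-week contrast, unadjusted | 80% | 80% |
| One-week contrast, baseline-adjusted | 87 / 90 / 94% | 87 / 90 / 94% |

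**5. Complete cases: numbers.** 15% of 95 is about 14 people, leaving 95×0.85 = 80.75, about 81, with power 0.80 for the one-week contrast. If 15% is the whole incomplete fraction, power is as planned. The issue is then bias and the ITT promise.

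**6. Complete cases: bias.** Let the log-odds of loss rise by 0.6 or 1.2 per SD of week-1 distress.
- Random loss: no bias.
- Same rule in both arms, no treatment effect: no bias in the comparison.
- Same rule in both arms, true effect 0.63, 15% lost overall: at slope 0.6, loss is 17% in the control arm and 13% in the MBCTp arm. Retained means fall by 0.099 and 0.073 SD, so the one-week effect shrinks by 0.025 SD. At slope 1.2, loss is 19% and 11%, the falls are 0.188 and 0.114, and the effect shrinks by 0.074 SD.
- One arm only, no true effect, 15% lost per arm: the one-week complete-case bias is 0.086 SD (slope 0.6) or 0.152 SD (slope 1.2). On the three-visit mean this is multiplied by (1+2r)/3: from 0.086×0.600 = 0.05 to 0.152×0.733 = 0.11 SD. The sign depends on which arm loses its more distressed members.

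**The case against.** The strongest defence is that the wording fits an ordinary pre-test plus three post-tests ANOVA. The hypothesis speaks of a decrease, the baseline questionnaires are repeated, and within-group differences are to be tested. On that reading the group-by-time test has 76% to 92% power for a sustained effect and 72% to 89% for a fading one, roughly the design power in both cases. This stands. A reader might infer from the 5% figure that the trial cannot detect a lasting benefit. The documents do not support that, because the figure belongs to one of several readings. What remains is that the plan does not say which reading applies.

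A reader might also infer that the plan prescribes dropping incomplete cases. It does not: no SPSS procedure is named, and listwise deletion is inferred from how repeated-measures ANOVA is normally run. The SAP also says that its analyses are outlined in the Appendix 3 flow diagram, which is not shown, so the omissions can be asserted only for the readable text.

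One-arm distress-linked loss has no support in the documents and is an illustration. The bias of 0.09 to 0.15 SD applies to a one-week complete-case contrast that the ANOVA does not plan; the three-visit mean is the nearest planned term. Conversely, it is tempting to say that loss working alike in both arms is harmless. That holds only if treatment has no effect.

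Finally, a missing-data rule, a named term and a stated role for baseline would close the gap without this particular model. That is fair, but the mixed model settles missing visits and baseline together.

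**Conclusion.** The concern holds and should be fixed. ITT is promised and 15% attrition expected, yet the only between-arm test of DASS-21 normally excludes anyone with a missing occasion, and the readable SAP gives no rule to prevent that. The treatment term is not named, neither candidate is the contrast the trial is sized on, and no baseline adjustment is stated.

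The size depends on the reading. Power runs from 5% to 95% for a sustained effect and from 38% to 89% for a fading one. The loss arises when baseline is not a time level and the term chosen does not match the shape of the effect. Complete-case bias runs from none (random loss) through a shrinkage of 0.025 to 0.074 SD at one week (same distress-linked rule in both arms, effect 0.63) to 0.05 to 0.11 SD on the three-visit mean (one arm only).

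The omissions are read from the text. The correlations, effect shapes and loss mechanisms are assumptions. It is not shown that the trial's result will be biased, only that the plan leaves it exposed.

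**What to change.** For DASS-21 and the other scale outcomes, replace the ANOVA with a linear mixed model (SPSS MIXED) containing visit, arm-by-visit, baseline and baseline-by-visit, with unstructured covariance and Satterthwaite degrees of freedom. Include every randomised participant with any post-test, in the assigned arm.

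State one primary between-arm contrast before the data are seen. The one-week difference matches the Sample size section, but the sponsor must reconcile it with the hypotheses, which list all three visits as primary. The sponsor must also say whether the DASS-21 total or a particular subscale is primary. Report the other visits with 95% confidence intervals.

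The mixed model does not protect against loss that depends on unseen scores. Add one not-at-random sensitivity analysis, for example multiple imputation with a stated shift in the imputed scores, increased until the conclusion changes. Keep the complete-case ANOVA as a sensitivity analysis only.

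The cost is revised SAP wording and slightly more analysis work, with no new data and no change in sample size.

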- Secondary outcomes: Greater improvements in emotion regulation, psychological flexibility, psychosocial functioning, re-hospitalization rate and psychotic symptoms at 1-week, 3-month and 6-month follow-ups post-treatment.

Method

Design

A randomized controlled trial, using a repeated-measures, two-group design, will be conducted to test and compare the effects of MBCTp in addition to treatment as usual (TAU) and TAU with PEp for people with recent-onset psychotic disorders (according to DSM-V) residing in the community over a 6-month follow-up.

Sampling and study settings

The study will be conducted in Integrated Community Centers for Mental Wellness (ICCMW). The Social Welfare Department has implemented this service in all the districts across the territory since 2010. It aims at enhancing the social support and re-integration of the ex-mentally ill persons into the community. It is a one-stop service providing social rehabilitation services ranging from early prevention to risk management for discharged mental patients, people with suspected mental health problems, their families and carers. There are 26 centers established across the 18 districts in Hong Kong till 2016.

Inclusion criteria:

Participants will be people who were diagnosed with recent-onset psychosis and have follow-up at one of the ICCMW centres;

- (i) Participants are Hong Kong Chinese residents and aged above 18;
- (ii) Participants have a primary diagnosis of psychosis and/or other psychotic disorders met the Diagnostic and Statistical Manual DSM-V equivalent to or less than 5 years (The National Institute For Health and Care Excellence, 2014);
- (iii) Participants are mentally stable as assessed by the researcher and a psychiatrist to comprehend the education and training provided (a pre-recruitment briefing session for potential participants will be conducted to verify their ability to follow instructions and understanding in participation, and case files will be reviewed to ensure a stable medication regime for at least 6 months) in order to ensure their ability to make a valid consent;
- (iv) Participants are able to read and understand Cantonese or Chinese.

Exclusion criteria:

- (i) Participants have recently participated in (less than 3 months) or are receiving other structured psycho-education and/or psychotherapies;

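### The plan does not say which DASS-21 score, visit or ANOVA term decides the primary hypothesis, so its false-positive rate is undetermined

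*SAP*

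**What the plan says.** - **Score.** SAP, Outcome Evaluation: "The primary outcome will be the Depression Anxiety Stress Scale- Short form (DASS-21"). The section describes depression, anxiety and stress scales and does not say whether the total, one scale or all three are tested.
- **Visits.** SAP, Study Aim, Objectives and Hypotheses: "Primary outcomes: Decrease in emotional distress at 1-week, 3-month and 6-month follow-ups post-treatment". The three visits have equal standing.
- **Model.** SAP, Design: "A randomized controlled trial, using a repeated-measures, two-group design". SAP, Data Analysis: repeated-measures ANOVA will "assess any significant differences on all dependent (outcome) variables within and between groups and across three post-tests". Neither group nor group-by-time is named as the deciding term.
- **Baseline.** SAP, Data collection procedure: outcomes "will be measured at one week post-intervention using the same set of questionnaires as the baseline measures". Baseline scores therefore exist, but the Data Analysis section does not make them an occasion or a covariate, or leave them out.
- **Level.** SAP, Data Analysis: "The significance level of all statistical tests will be set at 5" per cent. No order or adjustment follows.
- **Sample size.** SAP, Sample size: 82 participants (41 per group) for a between-group difference in emotional distress at post-intervention, effect size 0.63, power 0.80.

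**The concern.** The rule that turns data into a verdict on the primary hypothesis belongs in a SAP. Here the score, the visit, the model term and the role of baseline are all open, and every candidate test carries its own 5%. Several different results could each be reported as confirming the hypothesis, and the choice could be made after the data are seen.

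The same choices govern power. One ANOVA term may not test the expected pattern of benefit at all, depending on whether baseline is an occasion. A rule requiring all three visits is not the contrast for which the trial was sized.

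**Working it through.** **Inputs from the SAP.** 41 per group; effect size 0.63; level 0.05; power 0.80; three DASS-21 scales; three post-tests plus baseline. Outcome Evaluation prints "Depression-Anxiety 0.81; Anxiety-Stress 0.88 and Depression-Stress 0.83" as phi coefficients.

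**Assumptions, because the SAP gives no values.** Equal between-visit correlation ρ of 0.4, 0.6 or 0.8; complete data; independent participants; two-sided tests. The printed phi coefficients are read as between-scale correlations, with 0.6 as a lower alternative.

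**1. The plan's own figure.** Normal approximation: n = 2(1.960 + 0.842)²/0.63² = 39.6, so 40 per group. The t-test solution is 40.53, so 41 per group and 82 in all, with power 0.805. A one-sided calculation gives 32, so the stated size fits one two-sided 5% contrast. The 0.63 equals (0.76 + 0.50)/2, the midpoint of an effect on depression and anxiety and one on symptom-related distress, so it identifies no DASS-21 score.

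**2. False-positive rate on one score under no effect.** Simulation, 40,000 trials per setting, 41 per group:

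| Reading | ρ=0.4 | ρ=0.6 | ρ=0.8 |
|---|---|---|---|
| One pre-named test | 0.05 | 0.05 | 0.05 |
| All three visits, unadjusted | 0.0016 | 0.0054 | 0.0142 |
| Either ANOVA term, post-tests only | 0.098 | 0.098 | 0.099 |
| Either ANOVA term, baseline as occasion | 0.097 | 0.098 | 0.098 |
| Any visit, unadjusted | 0.132 | 0.122 | 0.100 |
| Any visit, baseline as covariate | 0.139 | 0.133 | 0.130 |

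Three independent tests would give 1 − 0.95³ = 14.3%. The hypothesis is a decrease relative to psychoeducation, so a result favouring psychoeducation cannot confirm it. Counting only results that favour MBCTp roughly halves these rates: about 5–7% for any visit, against 2.5% for one test.

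**3. If the subscales also count.** Any of nine scale-by-visit tests gives about 18–30% two-sided and 9–16% favouring MBCTp. These ranges cover unadjusted and baseline-adjusted tests and scale correlations from 0.6 up to the printed 0.81–0.88. Nine independent tests would give 1 − 0.95⁹ = 37.0%. Either ANOVA term on any subscale gives about 17–23%. These figures are illustrative, since the plan states no such rule.

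**4. What the ANOVA terms test.** Suppose a constant benefit of 0.63 at every post-test.
- *Post-tests only.* The arm difference is the same at each visit, so the group-by-time null hypothesis is true. Its rejection rate (0.051, 0.049, 0.051) is type I error. The group term has standardised effect 0.63/√((1+2ρ)/3) and power 0.954, 0.907, 0.856.
- *Baseline as a fourth occasion.* The arm differences are 0, 0.63, 0.63, 0.63. The group-by-time term now has power 0.761, 0.917, 0.998. The group term averages 3 × 0.63/4 = 0.4725, divided by √((1+3ρ)/4), and its power is 0.815, 0.712, 0.630.

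**5. Power by visit rule, same benefit.**

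| Rule | ρ=0.4 | ρ=0.6 | ρ=0.8 |
|---|---|---|---|
| 1 week, unadjusted | 0.807 | 0.805 | 0.805 |
| 1 week, baseline as covariate (effect 0.63/√(1−ρ²)) | 0.864 | 0.938 | 0.996 |
| All three visits, unadjusted | 0.599 | 0.641 | 0.687 |
| All three visits, baseline as covariate | 0.682 | 0.846 | 0.990 |

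Repeat runs move these by up to about 0.01, hence the ranges 59–69% for all three visits unadjusted and 86–99.7% for 1 week with the covariate.

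**The case against.** The strongest reply is that the plan is less open than it looks.

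- The sample size refers to post-intervention, a phrase that the SAP elsewhere attaches to one week. This points to 1 week as the visit that was sized. The primary hypothesis nevertheless lists three visits equally.
- Read literally, the word joining those visits requires all three. That keeps the error far below 5%, but it is not what the sample size powers.
- Data Analysis lists the occasions as the three post-tests, so baseline as an occasion is an extension of the text. Even so, the role of the collected baseline scores is not stated.
- The subscales might seem settled by "Clinical significance will be all subscales of DASS-21 shows a percentage improvement in mean scores". That sentence defines clinical significance by pre–post percentage change. It is not a between-arm decision rule.

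Three stronger readings are tempting and are not supported.

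- A reader might infer that the primary error is inflated to the any-of-nine figure. The plan states no rule that any one result suffices, one natural reading lies below 5%, and two-sided rates count results that could not confirm the hypothesis.
- A reader might call the sample size wrong. It is correct for the single contrast it names, and sizing on one contrast is normal.
- A reader might take the 5% for group-by-time as power. With a constant benefit and post-tests only, that term's null hypothesis is true.

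**Conclusion.** The concern holds as a gap in the decision rule. Nothing in the SAP fixes the score, visit or ANOVA term for the primary hypothesis, and the uniform 5% level supplies no order. Depending on the reading, the two-sided error on one score runs from 0.2% to 14%, around the nominal 5%. The supportable word is undetermined.

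The power consequence is equally concrete: the planned 80% applies to one post-intervention contrast and falls to 59–69% unadjusted if all three visits must be significant. If only the post-tests are modelled, the group-by-time term does not address a sustained, constant benefit. These sizes depend on the assumed correlations, complete data and independent participants. The subscale figures also depend on how the printed phi coefficients are read.

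This should be settled before the data are analysed.

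**What to change.** State one primary test: the two-sided 5% between-arm contrast on one named DASS-21 score (for example the total) at 1 week post-intervention, with the baseline score as covariate. Estimate it from a repeated-measures model with the three post-tests as occasions that keeps participants who miss a later visit, so that attrition at 3 and 6 months does not remove 1-week data. Test 3 months only if 1 week is significant, and 6 months only if 3 months is significant. Report the subscales, the omnibus group and group-by-time terms and the secondary outcomes as supportive.

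**Cost.** No extra data or participants are needed. The 1-week gate, the covariate and the sequence are design choices; the gate matches the contrast already sized. An isolated subscale, interaction or later-visit result would no longer count as primary success.

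Power at 1 week is about 80.5% unadjusted and 86–99.7% with the covariate, assuming complete data. The simulated error of the sequence under no effect at any visit is 0.050, 0.051 and 0.052 for ρ = 0.4, 0.6 and 0.8. It therefore holds 5% if participants are independent; clustering within the intervention groups is a separate matter.
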